As shown in Figure 3, proposed is a 2X2 factorial randomized clinical effectiveness trial testing the effects of combining CM as an adjunct to state-of-the-art, evidence-based CBT (CBT + CM vs. CBT only) and the effects of a single, long-term incentive for bioverified abstinence/no heavy drinking at 6-months follow-up (Long Term Incentive vs. No Incentive). All patients will be referred to standard aftercare and encouraged to participate in 12-step programs following the intervention. Use of aftercare and other health care utilization will be collected based on objective measures (VA electronic medical record) and participant report. Health-related quality of life will be collected at each follow-up. The primary endpoint (AIM 1) will be number of heavy drinking days in the past 30 days at the 6-month follow-up. Cost effectiveness analysis (AIM 2) will be performed using quality-adjusted life years (QALY) as the outcome. The utility of a long-term incentive (AIM 3) will be tested by examining use of aftercare and other alcohol-related treatment and heavy drinking days in the past 30 days at the 6 and 12-month follow-ups.

D.2. Patient Identification, Eligibility, and Recruitment

Patients will be identified from the Durham VA Health Care System (DVAHCS) using the hospital's computerized medical record. Records will be screened for AUD. After mailing introductory materials with an opt-out number, we will contact those who do not opt out via telephone to explain the study and recruit them for participation. If necessary, in order to reach female veterans, we can oversample women for the screening mailouts.

Figure 3. Trial Design

We will also utilize reactive recruitment methods as needed to reach potentially eligible veterans. For example, we will seek referrals from the DVAHCS Substance Use Disorders Clinic. In order to reach female veterans, we will seek referrals from the Women's Health Clinic. In addition, we will post IRB-approved flyers and brochures throughout the DVAHCS catchment area, especially in clinic areas and Vet Centers. In addition, we will post, if necessary, flyers and brochures in the community, in local restaurants, laundromats, university student centers, etc. We will also use online classified advertisements such as Craigslist.com to reach potential participants.

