Potential participants who discuss the study with study personnel will complete a brief phone screen to assess potential eligibility. Veterans who are potentially eligible will attend a screening session where they will complete diagnostic interviews, self-report measures, urine drug screen and alcohol breathalyzer to determine inclusion. Participants who screen in will be randomized at the first treatment session to one of two treatment conditions (CBT+mCM vs. CBT alone) and to one of two long term incentive conditions (abstinence incentive at 6 months vs. No incentive). Stratified permuted block randomization assignments will be performed using a computerized sequence generated by the study statistician before the study starts. The sequence will be password-protected so that only the statistician and other study staff who do not have patient contact will have access to the sequence. We will stratify on the presence of comorbid non-tobacco SUD.

D.4. Interventions

D.4.1. Cognitive-Behavioral Therapy for Substance Use Disorders

We will use the VA CBT for SUD protocol (DeMarce, Gnys, Raffa, & Karlin, 2014) to provide in-person treatment in both study arms. CBT will be provided by a therapist with at least a Master's degree in mental health (e.g., psychology, social work) who has reviewed CBT for SUD training materials. To prevent confounding from therapist effects, study therapists will treat cases in both study arms. CBT sessions will be weekly over 12 weeks as shown in Figure 3. Following the standard of care for AUDs, all participants will be referred to aftercare and encouraged to participate in 12-step programs following completion of the 12-session CBT intervention (Proctor & Herschman, 2014).

Figure 3. Timeline for Intervention and Follow-Ups

D.4.2. Mobile Contingency Management for AUD Procedures

As shown in Figure 3, participants will begin one week of practice mCM monitoring at session two of CBT so they can troubleshoot any difficulties they have using the app. The beginning of contingent reinforcement (i.e., the target quit date) is scheduled for the same date as session three of CBT (week 3), which will provide eight weeks of mCM before the end of CBT. Patients who attend all weekly appointments will have two sessions of CBT occurring after mCM ends to assist in preventing relapse when monetary reinforcement is removed.

Table 2. Virtual Scratch-Off Lottery Ticket Reinforcement Amounts				

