We plan to ask participants to report both gender and biological sex so that we can evaluate the role of biological sex on study outcomes. The association between sex and outcomes will be evaluated for all three aims. We will conduct sensitivity analyses to determine how variability in demographic/baseline variables influence estimates of treatment effects by analyzing and reporting the effects of randomization on males and females separately.

Multilevel modeling (MLM) will be used to analyze primary treatment outcomes (i.e., number of heavy drinking days; abstinence outcomes). MLM is appropriate for analyzing repeated-measures data; however, unlike ANOVA, MLM can accommodate data missing at random (Searle, Casella, & McCulloch, 1992). Because MLM takes into account the shared variance among observations within a given person, it can be used to leverage repeated measurements of alcohol use to enhance statistical power.

Although we do not anticipate much missing baseline data, we do anticipate missing values at post-treatment and each of the 6- and 12-month follow-ups due to attrition. Given evidence that maximum likelihood (ML) and multiple imputation (MI) provide the least biased results in comparison to last observation carried forward and worst-case scenario (i.e., missing=relapsed) in alcohol clinical trials under varying missing data assumptions (Hallgren & Witkiewitz, 2013), both approaches will be used here. MLM uses ML estimation; thus, missing values result in casewise—but not listwise—deletion. Consequently, participants with missing data will still be included in the analyses; estimates based on them will simply have a greater level of uncertainty. MI will be used to impute missing data using baseline demographic, clinical, and drinking measures. Regression parameter estimates will be computed for each imputation dataset and then pooled using Rubin's rules (Rubin, 1976). Sensitivity analyses will be conducted to determine how modeled treatment effects may vary by missing-data approach.

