Aim 1: To examine the first hypothesis that CM will be associated with greater treatment engagement and treatment completion than the control condition, treatment engagement will be defined as the number of counseling sessions completed, with treatment completion defined as completion of all 12 counseling sessions. Potential group differences in treatment engagement as a function of counseling sessions completed will be examined using independent *t*-tests. Contingency-table analysis will be used to examine whether a greater proportion of the CM participants complete the treatment in comparison to the control group. The second hypothesis is that CM will be associated with higher rates of self-reported abstinence and fewer heavy drinking days at 6 and 12 months. MLM will be used to model each of these outcomes. Specifically, logistic MLM will be

conducted to model abstinence as a function of treatment, time (categorized as end of treatment, 6 months, 12 months), and the interaction between treatment and time. Randomization to long-term abstinence incentive will be covaried. Linear contrasts will be specified at each time point to examine the hypothesis that CM will result in higher abstinence rates than CBT alone at 6 and 12 months. A similar count-based model (e.g., Poisson, negative binomial) will be conducted to analyze number of days of heavy drinking (per 30 days). In addition to modeling the effects of treatment, time, and the interaction between treatment and time, number of days of heavy drinking recorded at baseline and randomization to the long-term abstinence incentive will be covaried. Again, linear contrasts will be derived at each time point to compare treatment effects at 6 and 12 months.

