Aim 3: To examine the hypothesis that incentivizing long-term abstinence will increase AUD aftercare treatment utilization, enrollment in VA and/or non-VA alcohol treatment programs will be determined both in the first 6 months following randomization and the second 6 months leading up to the 12-month follow-up. Logistic MLM will be used to model treatment utilization during each of these intervals as a function of randomization to the long-term abstinence incentive, time, and the interaction between group and time. Randomization to CM will be covaried. Linear contrasts will be specified at each time point to examine the hypothesis that long-term incentives to promote abstinence will result in greater likelihood of AUD treatment utilization both prior to and following the 6-month incentive. To examine the hypothesis that long-term abstinence incentives will be associated with higher rates of self-reported abstinence and fewer heavy drinking days at 6 and 12 months, MLM analyses similar to those proposed for Aim 1 will be conducted. Specifically, logistic MLM will be used to model abstinence as a function of long-term incentive, time (categorized as end of treatment, 6 months, 12 months), and the interaction between incentive and time. Randomization to CM will be covaried. Linear contrasts will be specified at each time point to examine the hypothesis that a long-term incentive for abstinence will result in higher abstinence rates than no incentive at 6 and 12 months. A similar count-based model (e.g., Poisson, negative binomial) will be conducted to analyze number of days of heavy drinking (per 30

days). In addition to modeling the effects of long-term incentive, time, and the interaction between incentive and time, number of days of heavy drinking recorded at baseline and randomization to CM will be covaried. Linear contrasts will compare effects of the incentive at 6 and 12 months.

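### The plan asks how sex influences the treatment effects but provides only separate analyses in men and women, with no sex-by-arm estimate

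*Combined protocol and SAP*

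**What the plan says.** The combined protocol and SAP deals with sex in section F, just before the description of multilevel modelling. Gender and biological sex are both collected, "so that we can evaluate the role of biological sex on study outcomes". Two analyses follow.

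- **Sex as a predictor.** "The association between sex and outcomes will be evaluated for all three aims". No model is given for this.
- **Sex as a modifier of the treatment effect.** The plan promises "sensitivity analyses to determine how variability in demographic/baseline variables influence estimates of treatment effects", to be done by "analyzing and reporting the effects of randomization on males and females separately".

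The models later in section F do not mention sex. For heavy drinking days the Aim 1 text reads "In addition to modeling the effects of treatment, time, and the interaction between treatment and time", and then adds baseline heavy drinking and the incentive assignment as covariates. The Aim 3 text reads "In addition to modeling the effects of long-term incentive, time, and the interaction between incentive and time", and then adds baseline heavy drinking and the CM assignment. The abstinence models have the same structure without the baseline term.

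Sex is not a stratification factor. Section D.3 says "We will stratify on the presence of comorbid non-tobacco SUD" and names no other factor. The documents give no expected number of women. Section D.2 says that, if necessary, "in order to reach female veterans, we can oversample women for the screening mailouts", and it adds referrals from the Women's Health Clinic.

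**The concern.** Whether CM, or the long-term incentive, works differently in men and women is a question about a difference between two effects. Two separate analyses give two effects. They give no estimate of the difference, no interval for it and no test. The planned association between sex and outcomes does not fill the gap, because sex can predict drinking strongly while the treatment effect is the same in both sexes, and the reverse is also possible.

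What is at stake is how the sex-specific results will be read. When the two groups differ in size, the smaller one has less power, and a reader who sees significance in one sex and not in the other may infer a difference that the data do not show. The plan provides no other comparison to set against that inference. With sex unstratified, the balance of arms among women is also left to chance, so the number of women per arm matters for interpretation.

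**Working it through.** **Inputs from the documents (section F, power paragraph).** 140 participants with up to 3 observations each; ICC 0.20; 119, 101 and 86 participants remaining at end of treatment, 6 months and 12 months; effective sample size (ESS) 300 in full and 227 after attrition; detectable d = 0.43 with 90% power; d = 0.92 cited from a previous trial.

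**Assumptions.** Alpha 0.05 two-sided (not stated, but it reproduces the plan's 0.43, whereas one-sided gives 0.39); 1:1 allocation to CM within each sex; the same true effect in both sexes; women 10%, 20%, 30% or 50% of the sample.

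**The plan's own figures.** ESS is the sum over participants of m/(1 + (m − 1) × ICC), where m is the number of observations.

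- Full data: 420/1.4 = 300.
- After attrition, 86 people have three observations, 101 − 86 = 15 have two and 119 − 101 = 18 have one. This gives 258/1.4 + 30/1.2 + 18 = 184.3 + 25 + 18 = 227.3.
- Detectable d = (1.960 + 1.282)/√(227/4) = 0.430.

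Both agree with the protocol.

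**Separate analyses.** In a sex with n observations, the standard error of d is 2/√n, and power = Φ(d√n/2 − 1.96) + Φ(−d√n/2 − 1.96). The chance of significance in men only is P(men significant) × (1 − P(women significant)).

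Example with n = 101, d = 0.43 and 10% women:

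- Men: n = 90.9, d√n/2 = 2.05, power 53.6%.
- Women: n = 10.1, d√n/2 = 0.68, power 10.5%.
- Men only: 0.536 × 0.895 = 48%.

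Chance of significance in men only, with equal true effects:

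| Women (assumed) | n = 101, d = 0.43 | n = 101, d = 0.92 | ESS 227, d = 0.43 | ESS 227, d = 0.92 |
|---|---|---|---|---|
| 10% | 48% | 69% | 71% | 41% |
| 20% | 41% | 45% | 57% | 13% |
| 30% | 34% | 28% | 44% | 3% |
| 50% | 22% | 9% | 23% | 0.2% |

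At 50% women the reverse pattern, women only, is equally likely. A test of the sex-by-arm interaction gives a false difference 5% of the time under equal effects, by construction.

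**What the interaction can deliver.** Its standard error is √(4/n_men + 4/n_women).

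- n = 101, 10% women: √(4/90.9 + 4/10.1) = 0.663, so the 95% interval is ±1.30 d.
- n = 101, 20% women: √(4/80.8 + 4/20.2) = 0.497, so ±0.98 d.
- Power to detect a true sex difference of 0.43 is 10% and 14% in these two cases. At ESS 227 it is 16% and 25%.
- At ESS 227, the sex difference detectable with 80% power is 1.24 d, 0.93 d, 0.81 d and 0.74 d for 10%, 20%, 30% and 50% women.

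These are normal approximations on the d scale, as in the plan's own power statement. The planned models are logistic and count models, so the figures show size and are not exact.

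**The case against.** The strongest reply is that the plan does less harm than the table may suggest.

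- **A reader might infer that the plan cannot say anything about the role of sex.** The documents do not support that. The association between sex and outcomes is planned for all three aims and addresses sex as a predictor, although its model is unspecified. Two estimates with standard errors from independent groups would also let anyone calculate the difference; the plan just does not commit to doing so.
- **A reader might infer that the plan will compare a p-value in men with one in women.** It does not say so. The separate analyses are labelled sensitivity analyses, and no hypothesis or sample size rests on them. The risk of a false difference is therefore conditional on how the results are read.
- **A reader might infer that the protocol expects few women.** Section D.2 describes oversampling as a step to take if necessary, and the step would raise the share of women. A small female group is an assumption here, and the size of the problem depends heavily on it and on the true effect.
- **The interaction adds no women.** It will be imprecise, and if every term is interacted with sex the sex-specific effects will be close to the separate fits. Dropping the separate analyses would be a preference and not a necessity.

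All of this stands. It narrows the point without removing it: the question about effect modification is posed, and the only method named for it does not answer it.

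**Conclusion.** The point holds as a minor one. Section F asks how sex influences the treatment effects and provides no sex-by-arm term and no estimate of the male-female difference.

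If the separate results are read by significance, the chance of an apparent effect in men only, when the true effects are equal, ranges from 22% to 71% at d = 0.43 and from 0.2% to 69% at d = 0.92, across the assumed female shares and the two sample bases (101 participants or ESS 227). The width of these ranges reflects what the documents leave open, chiefly the number of women.

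The interaction estimate is the right contrast, but it can only be exploratory, and a non-significant interaction would not be evidence of equal effects. The primary analysis of heavy drinking days at 6 months is unaffected.

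**What to change.** In section F:

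1. Fit the planned Aim 1 models to all participants with sex and sex-by-CM (by time) terms added, as a supplement to the primary model. Do the same for Aim 3 with sex-by-incentive terms.
2. Report each interaction estimate with its 95% interval alongside the sex-specific effects, and give the number of women per arm. The separate analyses may be kept.
3. State that any conclusion about a sex difference will rest on the interaction estimate and not on which sex reaches significance.
4. Label the analysis exploratory, and say that a non-significant interaction does not show equal effects.
5. Name the model for the association between sex and outcomes.

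The cost is SAP wording and a few extra model runs. No new data, visits or participants are needed.

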Our long-term goal is to implement cost-effective treatments that reduce the morbidity and mortality associated with alcohol and substance misuse. VA has widely implemented evidence-based cognitive-behavioral therapy (CBT) for treatment of substance abuse disorders (Karlin & Cross, 2014). The primary goal of the current study is to evaluate the clinical effectiveness and cost effectiveness of CM as an adjunct to CBT for AUD. The trial will also explore the potential utility of a long-term abstinence incentive on treatment utilization and alcohol outcomes. We plan to conduct a comparative effectiveness trial with a 2 x 2 factorial design in which 140 veterans with AUD will be proactively recruited and randomized to receive either CM as an adjunct to state-of-the-art evidence-based CBT, or receive CBT alone; and to one of two long-term incentive conditions (i.e., receipt of a monetary incentive for abstinence/low-risk drinking at 6-months vs. no incentive). Specific aims include:

AIM 1: To evaluate the effectiveness of mobile contingency management, as an augment to evidence-based CBT for AUD, on (1) treatment engagement and retention, and (2) reduction in heavy drinking days and abstinence from alcohol at post-treatment, 6-month and 12-month follow-ups.

Hypothesis 1a: Mobile contingency management for AUD will be associated with greater treatment engagement and treatment completion.

Hypothesis 1b: Mobile contingency management for AUD will be associated with decreased self-reported heavy drinking days and increased rates of abstinence from alcohol at each follow-up.

AIM 2: To evaluate the cost effectiveness of CM as an adjunct to evidence-based CBT for SUD in quality adjusted life years (QALY).

Hypothesis 2: CM paired with CBT will result in greater cost-effectiveness compared to the CBT alone as measured by the incremental cost-effectiveness ratio.

AIM 3: To explore the effects of a long-term (six-month) abstinence incentive on (1) treatment utilization and (2) alcohol outcomes at the 6-month and 12-month follow-ups.

Hypothesis 3: A long-term abstinence incentive will (1) increase utilization of AUD aftercare and (2) be associated with reduced heavy drinking days and increased abstinence rates.

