Cost and Effectiveness Measurement. Our primary cost effectiveness outcome measure will be the incremental cost-effectiveness ratio (ICER), with costs as the numerator and effectiveness as measured by QALYs as the denominator. Costs will include: intervention delivery costs, participant time costs and health care costs as described above. The QALY is a standardized effectiveness measure, based on the EuroQol (EQ-5D5L), that allows for the comparison of the value of a particular intervention to a broad range of other potential health care investments. Differences in reduction in heavy drinking days and secondary drinking outcomes (e.g., abstinence) among veterans in the mCM+CBT and the CBT comparison group will allow us to identify changes in the QALY effectiveness measure across groups. To estimate the QALYs, we will employ the methods and estimates developed by Barbosa and colleagues (2010), who used a Markov model to assign utility weights to a range of drinking patterns for medical morbidity and mortality, adjusted for health-related quality of life. Incremental costs and effectiveness of mCM+CBT will be compared to those of the CBT comparison group.

D.7. Optional Study Procedure

One of our study therapists, [name], is seeking licensure as a Licensed Professional Counselor, and as part of her supervision, needs to provide video recordings of therapy sessions to her supervisor, [name], MS, LPCS for review. Data will be shared with [name] as view only in a Duke Box folder to which only [name], [name], and [name] have access. Data will be shared in accordance with a data agreement facilitated by Duke’s Office of Research Contracts, and signed by [name] and [name]. This study procedure is fully optional, and is indicated as such during the informed consent process.

D.8. Measures

Participants will complete measures at primary assessment time points (baseline, post-treatment, 6 months post-quit date, and 12 months post-quit date), as well as reporting on alcohol at each CBT session. Follow-ups will be completed in-person.

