D.8.7. Treatment Fidelity. Counselors will receive weekly supervision for CBT from [name] or another senior clinician. Following procedures recommended by the VA training program, we will utilize the Cognitive Behavioral Therapy for Substance Use Disorders Rating Scale to measure counselor adherence in delivering behavioral treatments for substance abuse disorders (Gnys, DeMarce, Raffa, & Karlin, 2014). A random selection of 10% of the counseling sessions will be rated for fidelity by rater who is otherwise independent of the conduct of the study. Fidelity ratings will be used in supervision to improve counseling. To measure therapeutic alliance, we will use the 16-item Individual Treatment Alliance Scale Revised Short Form, which has a demonstrated relationship with treatment dropout and treatment response in behavioral interventions (Pinsoff, Zinbarg, & Knobloch-Fedders, 2008). This measure will be given at the final treatment session for all participants, including participants who withdraw early from treatment.

D.8.8. Outcome Measurement and Biochemical Verification. At each treatment session, and at post-treatment and follow-ups, we will measure number of heavy drinking days (> 5 drinks in day for men, > 4 drinks in a day for women), binge drinking episodes (heavy drinking within a 2-hour period), number of drinking days, and drinks per drinking day. At follow-ups, we will conduct Timeline Follow-back interviews to improve self-reports of drinking behavior over the previous months. We will ask participants to complete items from the Addiction Severity Index (ASI) to assess the consequences of substance use on functioning in the previous month. Participants will complete all of the items of the Employment subscale, and items 1, 3, 7, 8, 9, 10, 28, 29, 30, 31, 32, and 34 of the Family/Social subscale. Early continuous abstinence will be defined as three consecutive weeks of alcohol abstinence in the first eight weeks after the quit attempt, a threshold that has been predictive of good long-term SUD outcomes (Carroll et al., 2014). We will bioverify self-reports of low risk drinking with fingerstick blood spot samples for PEth testing at 6-month and 12-month follow-ups.

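### The multiple-imputation model lists only baseline predictors, omitting the randomised arms and all post-baseline drinking, so it conditions on less than the likelihood analysis it is compared with

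*Combined protocol and SAP*

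**What the plan says.** Section F names ML and MI as the two approaches to missing outcomes and says that "both approaches will be used here". For ML it explains: "Consequently, participants with missing data will still be included in the analyses". For MI the only description of the imputation model is "MI will be used to impute missing data using baseline demographic, clinical, and drinking measures". The section also promises sensitivity analyses of how the treatment effect varies with the missing-data approach. The Aim 1 outcome models contain treatment, "time (categorized as end of treatment, 6 months, 12 months"), and their interaction, with the long-term incentive as a covariate. Session reports do not enter them.

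Section D.8.8 states: "At each treatment session, and at post-treatment and follow-ups, we will measure number of heavy drinking days". Section D.8 likewise describes assessments at the main time points "as well as reporting on alcohol at each CBT session". Table 3 is narrower: at treatment sessions it marks the BAM-C but not the Heavy Drinking Days or Timeline Follow-Back rows. Section D.3 says: "Participants who screen in will be randomized at the first treatment session". Anyone randomised should therefore have attended at least one session.

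Section D.10 gives a different rule, under which a missing outcome is counted as relapse or heavy drinking.

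**The concern.** An imputation model should contain every variable in the analysis model, and preferably those that predict both the outcome and its absence. The MI list falls short on both counts.

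- **Randomised factors.** If CM is not a predictor, imputed values carry no CM effect, and the estimated difference is pulled towards zero in proportion to the amount imputed. The same holds for the long-term incentive under Aim 3.
- **Post-baseline drinking.** Someone who drank heavily in treatment and then left is imputed at 6 months like a person with the same baseline who stayed. If such departures are commoner with CBT alone, the control arm looks better than it was.

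The planned comparison of approaches suffers too. When MI conditions on less than ML, disagreement may only reflect the missing predictors, and agreement reassures little. Using session data is the main thing MI could add to the multilevel model here, and the sentence as written gives it up.

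**Working it through.** **1. The plan's own figures (Section F, power paragraph).** N = 140, up to 3 visits, ICC 0.20, 15% attrition per visit.

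- No attrition: 140 × 3 / (1 + 2 × 0.20) = 300, as stated.
- With attrition: 119, 101 and 86 remain. By pattern, 86 have three visits, 101 − 86 = 15 have two, 119 − 101 = 18 have one. Effective size = 86 × 3/1.4 + 15 × 2/1.2 + 18 = 184.3 + 25 + 18 = 227.3, as stated.
- Detectable difference: (1.960 + 1.282) × √(4/227) = 0.430, as stated. Two-sided 5% is assumed, since the paragraph gives no alpha.

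I use 0.43 SD as the true CM difference below.

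**2. Who is missing, and what is known about them.** This assumes, as the plan's sequence implies, that those who leave do not return.

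| Missing at 6 months | n | Used by ML | Used by MI as listed |
|---|---|---|---|
| Post-treatment visit observed | 119 − 101 = 18 | baseline, arms, post-treatment | baseline |
| No post-treatment visit, session reports only | 140 − 119 = 21 | no outcome contributed | baseline |
| Total | 39 (28%) | | |

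At 12 months 140 − 86 = 54 (39%) are missing, 33 of them with at least one earlier visit.

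**3. Leaving out the arm.** With equal drop-out p in both arms and a balanced baseline, imputed values have the same mean in both arms. The estimate becomes (1 − p) × d = 0.72 × 0.43 = 0.31. Simulation gives 0.31 at correlations 0.2 and 0.5.

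**4. Leaving out on-treatment drinking.** Large-sample simulation with 400,000 per arm. The outcome is standardised normal; baseline, on-treatment, post-treatment and 6-month values share a common correlation. Drop-out is logistic in on-treatment drinking, slope 1 or 2 per SD. Regression imputation stands for the expected value of MI. Arm-specific drop-out, slopes and the normal outcome are my assumptions. Estimates of 0.43:

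| Drop-out, CBT alone vs CM | Correlation | Baseline, within arm | Baseline, no arm | Baseline + on-treatment, within arm |
|---|---|---|---|---|
| 28% vs 28% | 0.2 or 0.5 | 0.43 | 0.31 | 0.43 |
| 35% vs 21% | 0.2 | 0.40–0.42 | 0.29–0.30 | 0.43 |
| 35% vs 21% | 0.5 | 0.38–0.40 | 0.28–0.29 | 0.43 |

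The 35%/21% split averages the plan's 28%. A harsher 45%/25%, averaging 35%, gives 0.39–0.40 and 0.37–0.39 for baseline within arm.

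**5. MI against ML.** A second simulation lets people leave at each visit: 20% with CBT alone, 10% with CM, slope 1.5 on the most recent drinking. At 6 months about 36% and 19% are missing. For between-visit correlations 0.2 / 0.5 / 0.7 (with baseline 0.2 / 0.3 / 0.4):

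- MI from baseline and arm: 0.40 / 0.35 / 0.33
- ML, using post-treatment drinking: 0.42 / 0.39 / 0.38
- Adding session and post-treatment drinking: 0.43 throughout

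**6. Scale.** The standard error of the contrast is about √(4/227) = 0.13 on the plan's effective size. A shift of 0.03 is under a quarter of that; a shift of 0.43 − 0.31 = 0.12 is about nine tenths of it.

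**The case against.** The sentence does not say that nothing else may enter the model, and a competent analyst would probably include the arm. That is fair: the 0.31 is what the list yields if followed literally, not a forecast. But no other predictor is named anywhere, and an SAP is meant to settle this.

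A reader might infer that drop-outs' outcomes are imputed from baseline throughout, so that the primary result itself is biased. The documents do not support that. MI is one of two approaches, the Aim 1 contrasts are specified in the multilevel model, and ML keeps earlier visits. Session data are what both approaches leave out.

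A reader might also infer that early relapsers are always treated like those who stayed. Section D.10 would do the opposite, and under its rule extra drop-out with CBT alone would make that arm look worse. The direction of bias described here therefore applies to the MI in Section F only.

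Unequal loss at follow-up is not established. Hypothesis 1a reads "Mobile contingency management for AUD will be associated with greater treatment engagement and treatment completion"; Section F defines those outcomes by sessions completed, not attendance at 6 months, and follow-up visits are paid in both arms. Without unequal loss, and with arm in the model, the contrast is unbiased in these simulations.

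Nor is it settled that session heavy drinking days will exist as a variable, given Table 3. People who leave before session 3, the target quit date, have only pre-quit reports. Finally, at the plan's ICC the effect of omitting on-treatment drinking alone is small and conservative. That stands, although the 0.20 comes from 7-day point prevalence in a smoking trial and may not carry over to heavy drinking days.

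**Conclusion.** The concern holds for the MI analysis and for the planned comparison of ML with MI. Omitting the arm is the larger gap: 0.43 falls to about 0.31 with 28% missing, whatever the pattern of drop-out by arm, if the list is taken literally. Omitting post-baseline drinking costs about 0.01 to 0.03 SD at correlation 0.2 and 0.03 to 0.05 at 0.5 under the assumed 35%/21% split, and nothing under equal drop-out with arm included. These sizes rest on a standardised normal outcome and on drop-out driven by on-treatment drinking; the planned heavy-drinking outcome is a count. The point does not affect sample size or stated power. It should be corrected before analysis, but it does not undermine the primary analysis as such.

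**What to change.** Replace the imputation sentence with one such as:

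> 'The imputation model will include both randomised factors (CM and long-term incentive); baseline demographics, clinical status and drinking; heavy drinking days and abstinence at every observed assessment visit; a summary of session-level drinking (session heavy drinking days and/or BAM-C, for example the mean or the last observed value); and the number of CBT sessions completed.'

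Use a session summary rather than up to 12 separate counts, to keep the model stable with about 70 per CM arm. Leave out the breath results from the mobile app, which exist in one arm only. If imputation is run separately by CM arm, the long-term incentive must still be a predictor.

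Two reconciliations belong with this: the missing-data rule in Section D.10 with Section F, and Table 3 with Section D.8.8 on whether heavy drinking days are recorded at sessions. If only the BAM-C is recorded there, name it as the session predictor.

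The cost is one sentence and a somewhat larger imputation model. The change itself needs no new assessments and no more participants.
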